6.0 TRIAL FLOW CHART

		1st Week					Treatment Weeks										Follow-Up Weeks					Unscheduled		
Main Study Population 12-week Treatment		NA	NA	NA																				
Intensive Viral Kinetic subgroup	Screening	Day 1 ⁸	Day 2 ¹²	Day 3 ¹²	Day 5 ¹²	Day 7	2	4	6	8	10	12	14 ¹³	16 ¹³	FW4	FW8	FW 12	FW 16 ¹⁴	FW 20 ¹⁴	FW 24	HCV/HIV Viral Failure Confirmation Visit ^{9,10}	Early Discontinuation Visit ^{9,11}		
Visit No.	1	2	3	4	5	6	7	8	9	10	11	12	13	14	15	16	17	18	19	20	21	22		
Visit Windows	NA	NA	NA	+2d	-1 to +2d	-2 to +2d	-4 to +7d	-7 to +7d	-7 to +7d	-7 to +14d	-7 to +14d	-7 to +14d	-7 to +14d	-7 to +14d	-1 to +2 weeks					NA	NA			
ADMINISTRATIVE PROCEDURES																								
Informed Consent	x																							
Informed Consent for Future Biomedical Research (FBR)	x																							
Inclusion/Exclusion Criteria	x																							
Subject Identification Card	x																							
Medical History	x																							
Prior and Con-med Review	x	x				x	x	x	x	x	x	x	x	x	x						x	x		
Treatment Allocation		x																						
Review Study Medication Diary		x				x	x	x	x	x	x	x	x	x										x
Distribute Study Medication Diary		x					x	x	x	x	x	x ¹⁵	x											
CLINICAL SAFETY EVALUATIONS																								
Physical Examination ¹	x ¹	x ¹	x ¹	x ¹	x ¹	x ¹	x ¹	x ¹	x ¹	x ¹	x ¹	x ¹	x ¹	x ¹	x ¹	x ¹	x ¹	x ¹			x ¹	x ¹	x ¹	
Weight	x	x																						x
Height	x																							

		1st Week					Treatment Weeks										Follow-Up Weeks					Unscheduled					
			NA	NA	NA																						
	Screening	Day 1 ⁸	Day 2 ¹²	Day 3 ¹²	Day 5 ¹²	Day 7	2	4	6	8	10	12	14 ¹³	16 ¹³	FW4	FW8	FW 12	FW 16 ¹⁴	FW 20 ¹⁴	FW 24	HCV/HIV Viral Failure Confirmation Visit ^{9,10}	Early Discontinuation Visit ^{9,11}					
Visit No.	1	2	3	4	5	6	7	8	9	10	11	12	13	14	15	16	17	18	19	20	21	22					
Visit Windows	NA	NA	NA	+2d	-1 to +2d	-2 to +2d	-4 to +7d	-7 to +7d	-7 to +7d	-7 to +14d	-7 to +14d	-7 to +14d	-7 to +14d	-7 to +14d	-1 to +2 weeks					NA	NA						
12-Lead ECG	x						x	x		x		x		x	x								x				
Vital Signs	x	x				x	x	x	x	x	x	x	x	x	x	x	x			x			x				
Subject confirmation of birth control	x	x				x	x	x	x	x	x	x	x	x	x						x	x					
Review SAEs	x	x	x	x	x	x	x	x	x	x	x	x	x	x	x	x	x	x	x	x	x	x					
Telephone contact																		x	x								
LABORATORY SAFETY EVALUATIONS																											
Coagulation (PT & INR)	x	x				x	x	x	x	x	x	x	x	x	x		x			x	x	x					
Chemistry & Hematology	x	x				x	x	x	x	x	x	x	x	x	x	x	x			x	x	x					
HBsAg	x																										

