- ¹⁶ MK-3682 and MK-8408 open-label bottles provided by the SPONSOR cover a maximum of 18 days of dosing (2w + 4 days). An unscheduled visit must occur to get additional drug if the subject will run out of study drug prior to the next scheduled visit. Subjects should complete study therapy for all study drugs as defined by the length of the assigned treatment regimen.

Long Term Follow-Up Subjects with Virologic Failure	Follow-up Period					Unscheduled Visit
	Month					
	M12	M18	M24	M30	M36	
Visit Number	23	24	25	26	27	28
Visit Window	-3 to +3 months					NA
ADMINISTRATIVE PROCEDURES						
Long-Term Follow-Up Informed Consent ¹	x					
Review HCV Medications/Therapies	x	x	x	x	x	x
CLINICAL EVALUATIONS						
Focused Physical Examination (PE) ²	x		x		x	
Vital Signs (heart rate, blood pressure, temperature)	x		x		x	
Review Serious Adverse Events ³	x	x	x	x	x	x
LABORATORY SAFETY EVALUATIONS						
Coagulation (PT & INR)	x		x		x	
Chemistry & Hematology	x		x		x	
HCV EVALUATIONS						
HCV RNA ⁴	x	x	x	x	x	
Plasma for HCV Viral Resistance ⁴	x	x	x	x	x	

HCV = hepatitis C virus, INR = international normalized ratio, M = long-term follow-up month, PT = prothrombin time, SAE = Serious adverse event

- ¹ Subjects who take at least 1 dose of study drug, experience virologic failure, complete FW24, AND agree to participate in the long-term follow-up period of the study must sign a separate Informed Consent. This must occur prior to performing any procedures in the long-term follow-up period.
- ² A focused PE will be conducted when clinically indicated at the subject's annual visits.
- ³ Serious Adverse Events will be collected per requirements in Section 7.2; the reporting timeframe for serious adverse events is described in Section 7.2.3.1.
- ⁴ Blood samples will be collected for HCV viral resistance testing if the subject has quantifiable HCV RNA.

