8.4.1 Efficacy /Pharmacokinetics Endpoints

8.4.1.1 Efficacy Endpoints

An initial description of efficacy measures is provided in Section 4.2.3.1.

The primary efficacy endpoint is the proportion of subjects achieving SVR₁₂ after 12 weeks of treatment.

The secondary efficacy endpoints are:

- 1) the proportion of subjects achieving SVR₂₄ after 12 weeks of treatment.
- 2) the proportion of subjects experiencing virologic failure (either on-treatment failure or relapse post-treatment) at Follow-up Week 12 after 12 weeks of treatment, among all subjects who do not discontinue the study for non-treatment-related reasons.

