The mFAS population will be used for the efficacy endpoints of SVR₁₂ and SVR₂₄ as a supportive analysis and for the endpoint of the proportion of subjects experiencing virologic failure at FW12 as a primary analysis. The mFAS population is a subset of the FAS population, with subjects excluded for study discontinuation for reasons unrelated to the treatment regimen. Examples include loss to follow-up, discontinuation from the study due to non-drug related AEs, informed consent withdrawal, and other non-virologic failures.

The final determination on the exclusion of subjects from various analysis populations will be made prior to the final database lock and will be documented in a separate memo.

Subjects will be included in the treatment arm to which they are allocated for the analysis of efficacy data using the FAS, mFAS, and PP populations. Details on the approach to handling missing data are provided in Section 8.6, Statistical Methods.

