1. Treatment-Related Discontinuation = Failure (TRD=F) approach: Subjects with treatment-related missing data (type #2 above) will be considered as failure; whereas the subjects who have the non-treatment-related missing value (type #3 above) and who do not have virologic failure during the observed study period will be excluded from the analysis for the time points following their study withdrawal. Note that subjects with documented virologic failure during the treatment or follow-up period, even if they withdrew prematurely due to reasons not related to study drug, are classified as failures.
2. Missing=Failure (M=F) approach: Subjects with any non-intermittent missing data (i.e., type #2 and #3 above) will be imputed as failures, regardless of the reason for study discontinuation.

In addition, a missing baseline/Day 1 HCV RNA result will be replaced with a screening result, if available.

Proportions of Subjects With Virologic Responses and Virologic Failures

For the primary efficacy analysis, the proportions of subjects achieving SVR₁₂ after 12 weeks of treatment in each treatment arm will be provided and 95% confidence intervals for these rates will be calculated using the Clopper-Pearson method [49]. The same method will be used to analyze all binary endpoints including SVR₂₄ after 12 weeks of treatment.

For all analyses conducted using the PP and mFAS populations, the missing data approach of TRD=F will be utilized. In addition, for all analyses in these two populations, a subject will be considered to have achieved a particular endpoint if the HCV RNA levels for the infection he/she had at baseline are < LLOQ. In other words, if a subject has HCV RNA levels \geq LLOQ at a particular time point, but those RNA levels correspond to an infection that is of a different genotype and/or subtype compared to the infection detected at baseline and the baseline infection has been cleared, then the subject is considered to have achieved response for the given endpoint.

Sensitivity analyses that use the FAS population will utilize the M=F missing data approach. Also, in the FAS analyses, only subjects with HCV RNA levels < LLOQ for any type of HCV infection at a given time point will be considered to have achieved the endpoint.

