PP (Primary for SVR ₁₂ and SVR ₂₄)	HCV RNA < LLOQ for baseline infection HCV RNA ≥ LLOQ demonstrated to be due to reinfection (after clearance of baseline infection)	HCV RNA ≥ LLOQ for baseline infection*	Subject with important deviations from the protocol including subject discontinued from the study for non-treatment related reasons and other violations such as violation of I/E criteria, use of prohibited concomitant medications (see Section 8.5.1)
mFAS (Supportive for SVR ₁₂ , SVR ₂₄ ; Primary for proportion of subjects experiencing virologic failure at FW12)	HCV RNA < LLOQ for baseline infection HCV RNA ≥ LLOQ demonstrated to be due to reinfection (after clearance of baseline infection)	HCV RNA ≥ LLOQ for baseline infection*	Subject discontinued from the study for non-treatment related reasons.
FAS (Supportive for SVR ₁₂ and SVR ₂₄)	HCV RNA < LLOQ	HCV RNA ≥ LLOQ	Subject did not receive at least one dose of study medication
mFAS = modified Full Analysis Set FAS = Full Analysis Set PP = Per Protocol LLOQ = Lower limit of quantification *Baseline infection: Genotype(s) and subtype(s) present at baseline based on population sequencing and genotyping assay			

Subject Virologic Failure: Non-response, Rebound, Virologic Breakthrough, Relapse and Reinfection

Summary statistics will be provided to describe the rates of occurrence of subject non-response, rebound, virologic breakthrough, and relapse. Definitions for subject non-response, rebound, virologic breakthrough, and relapse are in Section 4.2.3.1.1.2. Reinfection will be defined as having detectable virus of a different genotype than that detected at baseline as determined by sequencing. Those with reinfection will be considered treatment success in the mFAS and PP analyses as long as the baseline infection was achieved HCV RNA < LLOQ.

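### Table 16, the mFAS definition and the virologic-failure endpoint exclude non-treatment-related withdrawals without sparing documented virologic failures, in conflict with TRD=F in Section 8.6.1

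*Combined protocol and SAP*

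**What the plan says.** Four places deal with subjects who leave the study for reasons unrelated to treatment.

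- **Section 8.6.1, TRD=F.** This approach is assigned to every PP and mFAS analysis. A subject with non-treatment-related missing data and no observed virologic failure "will be excluded from the analysis for the time points following their study withdrawal". Subjects with documented virologic failure, "even if they withdrew prematurely due to reasons not related to study drug, are classified as failures".
- **Table 16.** The PP row counts a "subject discontinued from the study for non-treatment related reasons" among important protocol deviations, and the mFAS row gives the same discontinuation as its only exclusion criterion. Neither row mentions documented failure or time points.
- **Section 8.5.1, mFAS.** The population is the FAS "with subjects excluded for study discontinuation for reasons unrelated to the treatment regimen".
- **Sections 3.2 and 8.4.1.1.** The FW12 virologic-failure proportion is taken "among all subjects who do not discontinue the study for non-treatment-related reasons".

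The supportive FAS analysis uses Missing=Failure. Its response rule is that only subjects with HCV RNA below LLOQ "for any type of HCV infection at a given time point will be considered to have achieved the endpoint". It says nothing about a failure documented earlier or about HCV therapy from outside the trial.

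**The concern.** Population membership is settled before any missing-data rule is applied. A subject removed from PP or mFAS cannot then be scored as a failure in it, so Table 16 and Section 8.6.1 cannot both be applied to a relapser who withdraws consent. PP is the primary population for SVR12 and SVR24, and mFAS is primary for the FW12 failure rate. The reported figure would therefore depend on which text the programmer follows.

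Withdrawal after relapse may not be unrelated to outcome. Section 4.2.1.3 says the trial includes no rescue medication, so a subject who has relapsed may have a reason to leave. Final population exclusions are to be decided before database lock. However, the trial is open-label and Section 8.2 allows SVR4 and SVR8 to be assessed during the study, so the ambiguity could be resolved with outcomes in view.

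In FAS the issue is different. Section 7.1.5.4 has relapsers return for their remaining follow-up visits. If one has started other HCV therapy and is suppressed at FW12 or FW24, the rule as written counts a response.

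**Working it through.** **Inputs.** PP sizes come from Section 8.9.1: 50 × 0.9 = 45 for Arms 1–4, and 25 × 0.9 = 22.5, given as about 22, for Arms 5–6. Intervals are two-sided 95% Clopper-Pearson. The number of relapsers who withdraw (k), and the number retreated outside the trial who return (m), are not in the documents. Both are assumptions and are varied below.

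**Step 1. The plan's own figures.** The lower limit is the 2.5% quantile of Beta(x, n−x+1) and the upper limit is the 97.5% quantile of Beta(x+1, n−x). This gives 41/45: 78.8–97.5; 43/45: 84.9–99.5; 20/22: 70.8–98.9. All eight rows of Table 19 reproduce to 0.1 point.

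**Step 2. Dropping documented failures.** Take an arm of n subjects with r relapsers, of whom k later withdraw for a reason recorded as non-treatment-related.

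- Section 8.6.1: SVR = (n−r)/n and virologic failure = r/n, whatever k is.
- Table 16, literal: SVR = (n−r)/(n−k) and virologic failure = (r−k)/(n−k).

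With n = 45 and r = 4 (the failure-rate column uses n = 45 for illustration, because the plan gives no mFAS size):

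| k | SVR12 (95% CI) | Virologic failure (95% CI) |
|---|---|---|
| 0 (same as 8.6.1) | 41/45 = 91.1% (78.8–97.5) | 4/45 = 8.9% (2.5–21.2) |
| 1 | 41/44 = 93.2% (81.3–98.6) | 3/44 = 6.8% (1.4–18.7) |
| 2 | 41/43 = 95.3% (84.2–99.4) | 2/43 = 4.7% (0.6–15.8) |
| 3 | 41/42 = 97.6% (87.4–99.9) | 1/42 = 2.4% (0.1–12.6) |
| 4 | 41/41 = 100% (91.4–100) | 0/41 = 0% (0–8.6) |

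With n = 22 and r = 2, one withdrawal moves SVR12 from 20/22 = 90.9% (70.8–98.9) to 20/21 = 95.2% (76.2–99.9).

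**Step 3. Dropping a responder.** A subject with observed SVR12 who leaves between FW12 and FW24 keeps that result under Section 8.6.1 but is removed altogether under Table 16. One such subject changes 41/45 = 91.1% to (41−1)/(45−1) = 40/44 = 90.9%. This part of the mismatch lowers SVR12 slightly.

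**Step 4. FAS.** If m relapsers are suppressed by non-study therapy at the time point, SVR goes from x/n to (x+m)/n, which is 1/50 = 2 points per subject in Arms 1–4 and 1/25 = 4 points in Arms 5–6. For illustration, 44/50 = 88.0% (75.7–95.5) becomes 45/50 = 90.0% (78.2–96.7) with m = 1 and 46/50 = 92.0% (80.8–97.8) with m = 2.

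**The case against.** The best defence is that Section 8.6.1 is the detailed rule and already handles the case. It introduces Table 16 as a summary, and Section 8.5.1 refers to Section 8.6 for missing data. The PP text in Section 8.5.1 removes non-virologic failures with administrative causes, and the mFAS examples end with other non-virologic failures. Both lean towards Section 8.6.1. TRD=F is also the stated method for the FW12 failure endpoint. A relapser who leaves because treatment failed could be classed as a treatment-related discontinuation for efficacy, which counts as failure anyway. All of this stands. It indicates which rule was probably intended, but no text says that Section 8.6.1 overrides the table, and the table and the mFAS sentence still lack the exception.

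A reader might infer that the plan does not carry documented failures forward and that SVR is therefore inflated. The documents do not support that. Section 8.6.1 carries them forward for PP and mFAS, and the time-point half of the mismatch works in the other direction.

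A reader might also see a contradiction in FAS, or conclude that retreatment would go unrecorded because the flow-chart row "Prior and Con-med Review" is blank at scheduled visits after FW4. The FAS rule is part of Section 8.6.1, so its silence is an omission. It affects a supportive analysis only, and Missing=Failure already fails a relapser who withdraws. Section 5.5 requires subjects to be asked about new drugs at each visit, and Section 7.1.1.5.2 requires medication taken during the trial to be recorded. The item "Review HCV Medications/Therapies" belongs to a long-term chart that starts at Month 12, so its closure under Amendment 04 removes nothing before FW24.

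**Conclusion.** The conflict between Section 8.6.1 and Table 16, the mFAS sentence and the endpoint wording is real and reaches the primary analysis. If the table were applied literally, each withdrawn relapser would raise SVR12 by about 2 points at n = 45 and about 4 points at n = 22, and would lower the failure rate by about 2 points at n = 45. A responder lost after FW12 would lower SVR12 by about 0.2 points. These sizes rest on assumed numbers of relapsers and withdrawals. The effect is zero if Section 8.6.1 governs or no relapser withdraws, so bias is possible but not established. The FAS gap is smaller and depends on retreatment outside the trial before the time point, for which the documents give no rate. This should be fixed, but it is not a critical defect: the intended rule is already written down.

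**What to change.** 1. In Table 16 (PP and mFAS rows), the mFAS sentence in Section 8.5.1 and the endpoint wording in Sections 3.2 and 8.4.1.1, restrict the exclusion for non-treatment-related discontinuation to subjects without documented virologic failure, and only for time points after withdrawal. This is the rule already in Section 8.6.1.
2. In the FAS paragraph of Section 8.6.1 and the FAS row of Table 16, state that documented virologic failure, or the start of non-study HCV therapy, before the time point counts as non-response.
3. Optionally, mark the medication review at FW8, FW12 and FW24 in the flow chart, so that it matches what Section 5.5 already asks for at each visit.

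The cost is wording only, with no new visits or samples. Reported SVR may be slightly less favourable than under a literal reading of the table.

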4.2.3.1.2 Viral Resistance Measurements

Resistance associated variants (RAVs) in the hepatitis C virus can lead to failure of therapy. This is one of the most important considerations when treating with a DAA. To better understand and document the potential for RAVs to impact treatment with MK-3682+MK-8408, blood samples for viral resistance assays are collected at Baseline (Day 1) to determine pre-existing RAVs to MK-3682 and MK-8408. Additional resistance testing on these samples may be performed. Blood samples for resistance testing are also collected during the follow-up period, as well as at the virologic failure confirmation visit (should this occur) for genotypic and investigational assays to assess emergence of resistance to MK-3682 and/or MK-8408 following treatment initiation. RAVs will be assessed for any subject who has detectable virus above 1000 IU/mL and has met a virologic failure criteria.

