7.1.3.3 HCV Evaluation

The following specimens are to be obtained as part of Efficacy/Pharmacogenetic Measurements:

- Samples for HCV Genotype evaluation must be obtained for inclusion in the study. All baseline samples will be genotyped using the FDA approved Abbott HCV Real Time Genotype II assay which detects HCV genotypes 1a, 1b, 2, 3, 4, 5, and 6 through the use of genotype-specific fluorescent-labeled oligonucleotide probes in a real-time RT-PCR assay. The RT-PCR reaction uses 3 sets of HCV specific amplification primers targeting the conserved 5'UTR (for all genotypes) and NS5B regions from GT1a and 1b. The assay has accuracy of >96% for GT1, 1a, 1b, 2, 3 and 4, 89% for GT5 and 83% for GT6 with 100% specificity in HCV serologically negative plasma samples. Phylogenetic analyses will be performed using sequences for NS3, NS5A and NS5B to ensure accurate assignment of sample genotype/subtype.
- Blood must be drawn from each subject to assess HCV RNA plasma levels at various time points as shown in the study flow chart. HCV RNA in plasma will be measured using a COBAS™ AmpliPrep/COBAS™ Taqman™ HCV Test, v2.0 ® assay with a lower limit of quantification (LLOQ) of 15 IU/mL. Leftover plasma may be used for viral resistance testing if needed. Also, leftover plasma may be used for future biomedical research only if the subject signed for future biomedical consent.
- Blood must be drawn from each subject to assess viral resistance mutation and processed as instructed by the central laboratory manual. Leftover plasma may be used for future biomedical research only if the subject signed for future biomedical consent.

- Protein and metabolites may be measured from blood samples to compare biomarkers measured prior to treatment, to biomarkers measured at several time points during treatment that correlate with subject response to treatment (e.g., sustained viral response).
- Samples collected for genetic analysis are obtained at Day 1. Any leftover DNA may be used for future biomedical research only if the subject signed for future biomedical research consent.

Note: Samples may also be used for future assay development and validation if the subject signed for future biomedical research consent.

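### Reinfection is defined in two conflicting ways, by genotype or by genotype and/or subtype, and both score a new infection of the baseline subtype as non-response in PP and mFAS; the bias is conservative and probably small.

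*Combined protocol and SAP*

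**What the plan says.** Section 8.6.1 separates clearing the baseline infection from being free of HCV. For PP and mFAS, Table 16 lists as a response "HCV RNA ≥ LLOQ demonstrated to be due to reinfection (after clearance of baseline infection"), and the text below the table adds that "Those with reinfection will be considered treatment success in the mFAS and PP analyses", provided the baseline infection was brought below LLOQ.

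Three places in 8.6.1 say how the new virus is told from the old one:

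- **Response rule** (text on proportions with virologic response). Once the original virus is gone, viraemia is disregarded if "those RNA levels correspond to an infection that is of a different genotype and/or subtype compared to the infection detected at baseline".
- **Table 16 footnote.** "Baseline infection: Genotype(s) and subtype(s) present at baseline based on population sequencing and genotyping assay".
- **Definition** (text below Table 16). "Reinfection will be defined as having detectable virus of a different genotype than that detected at baseline as determined by sequencing".

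The FAS analysis makes no such distinction: only subjects below "LLOQ for any type of HCV infection at a given time point will be considered to have achieved the endpoint".

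Two other sections bear on what could be done. Section 4.2.3.1.2 provides for resistance samples on Day 1, in follow-up and at failure confirmation, and says "RAVs will be assessed for any subject who has detectable virus above 1000 IU/mL and has met a virologic failure criteria". Section 7.1.3.3 says "Phylogenetic analyses will be performed using sequences for NS3, NS5A and NS5B to ensure accurate assignment of sample genotype/subtype".

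**The concern.** There are two defects.

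First, the definition names genotype only, while the response rule and the footnote also use subtype. A change of subtype within a genotype is therefore handled differently depending on which sentence the programmer follows.

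Second, neither wording can recognise a new infection with the genotype and subtype present at baseline. Such a subject has cleared the treated infection, which is what the PP and mFAS analyses set out to credit, yet is counted as a failure of the regimen. The endpoints touched are PP SVR12 (primary), PP SVR24, the mFAS virologic failure rate at FW12 and the descriptive relapse rate. Polymorphisms of a new strain could also be read as treatment-emergent RAVs in the exploratory summary.

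**Working it through.** **1. The wordings applied to the possible cases.** Take a subject with target not detected at end of treatment and confirmed HCV RNA at or above LLOQ in follow-up.

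| Baseline virus | Later virus | Response rule and Table 16 footnote | Definition below Table 16 |
|---|---|---|---|
| GT1a | GT3 | Response | Reinfection |
| GT1a | GT1b | Response | Not reinfection |
| GT1a | New GT1a strain | Non-response | Not reinfection |

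The second row is the conflict. The third is the gap: by the footnote, the new GT1a virus is the baseline infection. The relapse definition in 4.2.3.1.1.2 requires confirmed viraemia after target not detected at end of treatment and has no test of strain, so this subject is also a relapse. A subject with detected but unquantifiable RNA at end of treatment would be a non-response without meeting the relapse definition.

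**2. The plan's own precision.** Section 8.9.1 expects about 45 PP subjects in each of Arms 1 to 4 and 22 in each of Arms 5 and 6. Exact Clopper-Pearson limits reproduce Table 19: 43/45 gives 84.9% to 99.5%, and 20/22 gives 70.8% to 98.9%.

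**3. Effect of one misclassified subject.** 1/45 = 2.2 points and 1/22 = 4.5 points.

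| Scored as failure | Scored as response |
|---|---|
| 43/45 = 95.6% (84.9, 99.5) | 44/45 = 97.8% (88.2, 99.9) |
| 20/22 = 90.9% (70.8, 98.9) | 21/22 = 95.5% (77.2, 99.9) |

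**4. How often.** The documents give no reinfection rate. I assume 1 to 5 per 100 person-years, constant over follow-up. Expected reinfections of any type in an arm = n × rate × weeks/52.

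- n = 45, FW12: 45 × 0.01 × 12/52 = 0.10; at 0.05, 0.52.
- n = 22, FW12: 22 × 0.01 × 12/52 = 0.05; at 0.05, 0.25.
- By FW24 the window doubles: 0.21 to 1.04 and 0.10 to 0.51.

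Only the same-subtype share is misclassified. That share is not given either, so these are upper figures for the assumed rates.

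**5. The sentinel rule (8.7).** It counts relapse by FW4 among the first 10 PP subjects. Expected reinfections are 10 × 0.01 × 4/52 = 0.008, or 0.04 at 0.05. Even if all were same-subtype, the failure probability becomes (1 − SVR) + SVR × rate × 4/52. The chance of 3 or more of 10 then goes from 7.0% (Table 18) to between 7.1% and 7.6% at a true SVR of 90%. At 95% it goes from 1.2% to between 1.2% and 1.4%.

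**The case against.** The strongest reply is that this is a choice and not a slip. The plan says what it means by baseline infection: genotype and subtype. That rule is objective and needs no judgement. Its error lowers SVR, which is the safe direction in an open-label, sponsor-analysed estimation study. A sequence criterion would move viraemic subjects to success in the primary analysis using a threshold the documents do not supply, and FAS already gives a result that does not depend on the definition.

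Much of this stands: the direction is conservative and FAS is untouched. It does not remove the conflict between the wordings. It is also met by fixing the criterion before database lock, defaulting to relapse and showing both counts.

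A reader might infer more than the documents support:

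- **That same-subtype reinfection is likely here.** Section 4.1.1.1 describes regional genotype distribution but gives no re-exposure probability. Section 5.5 admits subjects on stable opiate substitution only if not excluded by criterion 10 of 5.1.3, which bars clinically relevant drug or alcohol abuse within 12 months of screening.
- **That it could trigger the sentinel rule.** Step 5 shows a negligible effect.
- **That the resistance objective is corrupted.** Emergent RAVs are an exploratory endpoint (8.4.1.3). The secondary resistance objective concerns baseline RAVs and is touched only through SVR12 scoring.
- **That all the sequences already exist.** RAV assessment at failure is limited to virus above 1000 IU/mL, and the phylogenetic work in 7.1.3.3 appears under genotyping of baseline samples, for typing. That paired sequences can separate strains of one subtype is a reasonable inference, which the documents do not state.

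**Conclusion.** The point holds as a worthwhile clarification of the SAP. The two wordings conflict on a change of subtype, both miss same-subtype reinfection, and no section plans a strain-level comparison.

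The bias is downward. On the assumed rates, fewer than one reinfection of any type is expected per arm by FW12, and about one at most by FW24 (1.04 in an arm of 45 at the upper rate). If a case does occur, it costs 2.2 points of SVR12 in Arms 1 to 4 or 4.5 points in Arms 5 and 6. The frequencies rest wholly on the assumed rate; the per-case effects rest only on the planned PP sizes. The documents do not support calling this a threat to the trial's conclusions.

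**What to change.** Amend 8.6.1 before database lock:

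1. Make the response rule, the definition and the Table 16 footnote say the same thing.
2. Decide reinfection versus relapse by phylogenetic comparison of paired baseline and failure NS5A/NS5B sequences against a fixed criterion, whatever the genotype.
3. Default to relapse when the failure sequence is missing (for example at or below 1000 IU/mL) or ambiguous.
4. Leave the FAS rule as it is.
5. Report PP and mFAS results with same-subtype reinfections counted both ways.
6. Exclude confirmed reinfections from the exploratory emergent-RAV summary.

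The cost is SAP wording and a small extension of planned laboratory work: the phylogenetic analysis must explicitly cover failure samples. A clustering criterion has to be chosen in advance, and failures with low viral load will stay unclassified.
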